5.3.8 Exploratory Efficacy Analyses

Exploratory secondary efficacy endpoints will only be summarised descriptively by visit and treatment group unless otherwise specified below.

Double-blind treatment period

Absolute change from baseline in Blood Gas and Lung Function Tests

Absolute change from baseline of (A-a)DO₂, VC (% predicted), DLCO (% predicted), FEV₁ (% predicted), FVC (% predicted), and relative change from baseline of PaO₂ after 4 and 12-weeks treatment will be summarised by visit according to description in previous sections.

Time period during which the (A-a)DO₂ level is maintained below Baseline minus 10mmHg

This time period will be defined as the difference between the date of the visit where the (A-a)DO₂ level first reaches below the baseline level minus 10 mmHg and the date of the first visit where the where the (A-a)DO₂ level first reaches above the baseline level minus 10mmHg. For subjects never reaching the first threshold before ending the double-blind treatment period, the time period will be set to zero, and for subjects never reaching the second threshold, the time period will be set to the duration between the visit where the first threshold it reached and the last visit of the double-blind treatment period. This time period, in days, will be summarised descriptively.

Number of subjects with improved tolerance to exercise

Number of subjects with improved tolerance to exercise (increase in distance walked ≥ 50 m (compared to baseline) or desaturation < 4 percentage points on the 6MWT, respectively) after 4 and 12-weeks treatment will be summarised by visit according to description in previous sections.

Time period during which the improvement in tolerance to exercise is maintained

The time period during which the improvement in tolerance to exercise is maintained will be defined as the difference between the date of the visit where subjects are for the first time classified as having improvement in tolerance to exercise, defined as increase in distance walked ≥ 50 m (compared to baseline), and the date of the first visit where the increase in distance walked is above ≥ 50 m compared to baseline on the 6MWT. This time period, in days, will be summarised descriptively.

Dyspnoea score and cough scores

Change from baseline in dyspnoea score and cough scores (severity and frequency) after 4 and 12-weeks treatment will be summarised as described in previous sections for 24 weeks of treatment.

Number of subjects with improved QoL (change of ≥ 4 units on the SGRQ) The St Georges Respiratory Questionnaire (SGRQ) was described under Key secondary efficacy endpoints. The three derived domain scores and total score, and the corresponding changes from baseline will be summarised by visit. Individual item responses will be listed.

Subjects who have an improvement of more than 4 units from baseline on the SGRQ total score will be counted by visit and treatment group. The number of subjects with improvement of more than 4 units from baseline on the SGRQ total score will be summarised in the way that other categorical data are summarised.

Number of subjects with 'no problems' in EQ-5D after 4, 12, and 24-weeks treatment

The EuroQoL-5D (EQ-5D) will be used to measure health outcome in terms of mobility, self care, usual activities, pain/discomfort, anxiety/depression. The 5 level instrument (EQ-5D-5L) which uses a 5-point scale (no problems, slight problems, moderate problems, severe problems, and extreme problems) will be used in the local language. A VAS-scale is also included in the EQ-5D questionnaire. Each dimension/item score and the number of subjects in each state will be summarised by visit including the corresponding change from baseline.

Number of subjects where each item on the EQ-5D are scored with the highest outcome, indicating no problems, will likewise be counted by visit and treatment group. The number of subjects with each item, scored as “no problems” on EQ-5D will be summarised in the way that other categorical data are summarised.

Change in serum concentration of possible biomarkers

The possible biomarkers KL-6, CEA, SP-A, SP-B , SP-C, SP-D, Cyfra 21-1 and LDH will be summarised by visit after 4, 12, and 24-weeks treatment including both observed values and change from baseline.

Levels of anti-drug antibodies (anti-GM-CSF, anti-Polyethylene glycol (anti-PEG) and anti-recombinant Human Albumin (anti-rHA)

Number of subjects with and without measured anti-drug antibodies (positive/negative), number of subjects with neutralising antibodies where tested, actual anti-drug antibody titers, and any titer increase or decrease >2 or >4 fold over baseline titer, will be summarised by visit using standard descriptive summary statistics.

Sampling for anti-drug antibodies in France is more frequent than for the other countries, thus additional summaries only including data collected in France will be prepared.

Similar summaries will be done for double-blind treatment period and the Follow-up period.

Change in serum concentration of GM-CSF post first dose of trial drug and after 4-weeks treatment

Pre and 2h post dose serum concentration of GM-CSF, and the corresponding changes (2h post dose measurement – pre dose measurement) will be summarised for first dose of trial drug and after 4 weeks of treatment.

In US sites, additional sampling is done 12 and 24 weeks after randomization, and at week 12 during follow-up, including pre and 2h post dose. These US sampling data will be summarised separately, in the same way as described above.

For sites in Japan additional sampling is done, including pre-dose and samples at 1, 2, 4 and 8 hours post dose. These sampling profiles for Japan will be summarised separately. If applicable (sufficient number of samples have GM-CSF concentrations above LLOQ) standard PK parameters will be derived and evaluated, and the results will be provided in a separate PK-report.

Number of subjects in need for oxygen supplement therapy

Number of subjects in need for oxygen supplement therapy, will be summarised by visit during 24-weeks treatment. The number of subjects in need for oxygen supplement therapy will be defined based on actual use of oxygen supplementation as recorded in concomitant therapy. Oxygen therapy will be summarised separately according to start and stop date of therapy, in the same way that other concomitant medication is presented. Proportion of subjects with supplemental oxygen therapy will be compared between treatment groups using a logistic regression model including treatment, baseline use of supplemental oxygen therapy, strata, and Japan vs Other countries.

The distribution of DSS at Screening and at Week 24

Shift tables will be produced for observed DSS scores at Screening/Baseline vs Week 24, displaying both the visit distributions and the shifts between visits. Similar shift tables will also be produced displaying number of subjects with a DSS score of 1 or 2, vs number of subjects not reaching a DSS score of 1 or 2.

Follow-up period

The following endpoints related to visits in the follow-up period will be summarised, both by randomised treatment during the double-blind treatment period and in total, in the same way that the corresponding endpoints during the double-blind treatment period is summarised.

- Number of subjects requiring WLL, or other treatment for aPAP and number of treatment courses required during 24 and 48-weeks follow-up
- Time to WLL, or other treatment for aPAP during 24 and 48 weeks follow-up
- Absolute change from baseline in (A-a)DO₂ and VC (% predicted), DLCO (% predicted), FEV₁ (% predicted), FVC (% predicted), and relative change from baseline of PaO₂ after 12, 24, 36 and 48-weeks follow-up
- Number of subjects with improved tolerance to exercise (increase in distance walked ≥50 m (compared to baseline) or desaturation <4 percentage points on the 6MWT, respectively) after 12, 24, 36 and 48-weeks follow-up
- Levels of anti-drug antibodies (anti-GM-CSF, anti-Polyethylene glycol (anti-PEG) and anti-recombinant Human Albumin (anti-rHA)) after 12 and 24 weeks follow-up
- The distribution of DSS after 24 and 48-weeks follow-up
- The percentage of subjects with DSS 1 or 2 after 24 and 48-weeks follow-up

In addition to the above endpoints described in the protocol, (A-a)DO₂ values collected during the follow-up period will be summarised only including values assessed based on arterial blood gas samples, excluding capillary samples.

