6.3 Exploratory Objectives

6.3.1 Double-blind treatment period

- To compare efficacy of inhaled molgramostim with placebo on (A-a)DO₂, VC, DLCO, FEV₁, PaO₂, and on tolerance to exercise after 4-weeks and 12-weeks treatment
- To compare the duration of response of inhaled molgramostim with placebo in (A-a)DO₂ and tolerance to exercise
- To compare efficacy of inhaled molgramostim with placebo on dyspnoea and cough after 4-weeks, and 12-weeks treatment
- To compare efficacy of inhaled molgramostim with placebo on Quality of Life (QoL) after 4-weeks, 12-weeks, and 24-weeks treatment

- To assess pharmacodynamic effects on selected biomarkers in serum after 4-weeks, 12-weeks, and 24-weeks treatment of inhaled molgramostim or placebo
- To assess effect of molgramostim on Granulocyte Macrophage Colony Stimulating Factor (GM-CSF) concentration in serum after the first dose and after 4-weeks treatment and to assess levels of antibodies to GM-CSF after 4-weeks, 12-weeks and 24-weeks treatment with molgramostim or placebo
- To assess the requirement for oxygen supplementation therapy during 24-weeks treatment with molgramostim or placebo
- To assess the change in Disease Severity Score (DSS) from Screening to Week 24

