5.3.6 Primary Efficacy analysis

The primary efficacy variable, (A-a)DO₂, will be collected at Screening, Baseline (randomisation), Week 4, 12 and 24 during treatment period, and at Week 12, 24, 36 and 48 during the follow-up period. All (A-a)DO₂ values reported in the CRF will be recalculated for statistical analyses using the equation:

$$Aa\ Gradient = \left(F_i O_2 (P_{atm} - P_{H_2O}) - \frac{P_a CO_2}{0.8} \right) - P_a O_2$$

where F_iO₂ is fraction of inspired oxygen

P_{atm} is ambient atmospheric pressure

P_{H₂O} is saturated vapour pressure of water at body temperature (set to 47 mmHg / 6.266 kPa)

P_aCO₂ is arterial partial pressure of carbon dioxide

P_aO₂ is arterial partial pressure of oxygen

Any of these assessments reported in kPa will be converted to a result in mmHg before the calculations, this will be done using a factor k=7.5.

The primary efficacy endpoint, absolute change from baseline of (A-a)DO₂ after 24-weeks treatment, will be analysed based on an ANCOVA model including treatment group, WLL (stratification), Japan vs other countries, and baseline (A-a)DO₂. The data from the three treatment groups will be analysed all together (all treatment groups included in one model). Contrasts will be set up to estimate treatment differences in change from baseline with 95% confidence intervals (CI) and the corresponding p-value for Molgramostim OD vs. Placebo and for Molgramostim intermittently vs. Placebo.

For each analysis two sided tests will be performed where the null hypothesis is that there is no difference between treatment groups, which will be tested against the alternative that

there is a difference. Control for type-1 error inflation due to multiple testing will be handled as described in section 5.4.

A de-facto estimand approach will be applied, where for the primary analysis, all observed data will be included, irrespective of subject adherence to the randomised treatment. Subjects who withdraw from their randomised treatment before week 24 will be followed up through to week 24, and their week 24 data will be considered as primary, irrespective of treatment discontinuation, treatment interruption(s), use of rescue medication (WLL or other), etc.

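### The (A-a)DO2 duration-of-response rule in SAP 5.3.8 cannot register the Week 24 result: a loss first seen at Week 24 scores the same as a response still present then

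*SAP*

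**What the plan says.** Among the exploratory objectives, Protocol 6.3.1 lists: "To compare the duration of response of inhaled molgramostim with placebo in" (A-a)DO2 and exercise tolerance. The protocol leaves the analysis to the SAP, so the derivation in SAP 5.3.8 is the working definition.

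For (A-a)DO2, the period starts at the first visit below baseline minus 10 mmHg. It ends at the first visit where the "level first reaches above the baseline level minus 10mmHg". Two special cases follow:

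- Never responded: "For subjects never reaching the first threshold before ending the double-blind treatment period, the time period will be set to zero".
- Never lost: "for subjects never reaching the second threshold, the time period will be set to the duration between the visit where the first threshold" was reached and the last double-blind visit.

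The days are then summarised descriptively. Nothing marks a response as ongoing or censored.

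SAP 5.3.6 says that (A-a)DO2 "will be collected at Screening, Baseline (randomisation), Week 4, 12 and 24 during treatment period". The flow chart in Protocol 7.2.2 agrees: there is no (A-a)DO2 at Weeks 8, 16 or 20. SAP Appendix 1 lists one output for this duration, Table 14.2.4.1.

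**The concern.** A duration endpoint should tell a response that lasted from one that did not. Here the last assessment of (A-a)DO2 falls on the visit used as the end date when response is never lost. A loss found at that visit and a response still present at it both end on the same date.

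Week 24 matters for two reasons. Protocol 5.2 cites 24 weeks as the time to maximum gas-exchange response, after a lag of 4 to 12 weeks, so late responders are to be expected. Protocol 10.1.1 makes arterial sampling mandatory at Week 24 but lets experienced sites use capillary samples at Weeks 4 and 12. Apart from baseline, the duration thus rests on results from the two visits where capillary sampling is allowed.

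At stake is whether Table 14.2.4.1 can answer its objective. No confirmatory test is involved.

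**Working it through.** The documents give no figure for this endpoint, so there is nothing to reproduce. The check applies the rule to every possible response pattern.

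**Inputs.** Nominal visit days after randomisation, from Protocol 7.2.1: Week 4 = 28, Week 12 = 84, Week 24 = 168, each ±7 days. R means below baseline minus 10 mmHg and - means above it, in the order Weeks 4, 12, 24. Loss is sought only after the first response.

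**SAP rule.** Days = (first non-responding visit after onset, or day 168 if none) minus (first responding visit).

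**Midpoint rule**, for comparison. Onset and first loss are placed midway between adjacent assessments: (0 + 28)/2 = 14, (28 + 84)/2 = 56, (84 + 168)/2 = 126. A response not lost ends at day 168.

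| Pattern | SAP rule | Midpoint rule | First response at Week 24 |
|---|---|---|---|
| RRR | 168 - 28 = 140 | 168 - 14 = 154 | ongoing |
| RR- | 168 - 28 = 140 | 126 - 14 = 112 | lost |
| -RR | 168 - 84 = 84 | 168 - 56 = 112 | ongoing |
| -R- | 168 - 84 = 84 | 126 - 56 = 70 | lost |
| R-R | 84 - 28 = 56 | 56 - 14 = 42 | lost at Week 12 |
| R-- | 84 - 28 = 56 | 56 - 14 = 42 | lost at Week 12 |
| --R | 168 - 168 = 0 | 168 - 126 = 42 | ongoing |
| --- | 0 | 0 | no response |

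Under the SAP rule the eight patterns give four values, and each value is shared by two patterns that differ only at Week 24.

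**Robustness.** Each visit was shifted by -7, 0 or +7 days (27 combinations), with Week 4 and Week 12 each responding, not responding or missing (9 combinations). In all 27 × 9 = 243 cases the duration with response at Week 24 was compared with the duration without it. There were no differences.

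**Wording.** The SAP does not say that the second visit must come after the first. Taken literally, the first visit above the level could precede the response. Then -RR and -R- both give 28 - 84 = -56 days, and --R gives 28 - 168 = -140 days.

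**The case against.** Several points on the other side stand.

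- **Scope.** A reader might infer that lost and sustained responses always score alike. They do not: a loss seen at Week 12 scores 56 days against 140 for a response kept throughout.
- **Ordering.** A reader might infer that the rule misorders subjects, since RR- scores 140 and -RR, still responding, scores 84. The documents do not support that. The midpoint rule gives both 112. With one change of state between visits, the true first response could last 56 to 168 days for RR- and 84 to 140 days up to Week 24 for -RR. The ranges overlap, so the 56-day gap is unjustified, but it is not a proven reversal.
- **Regained response.** R-R scoring the same as R-- follows from an endpoint about a maintained response that ends at first loss. That is a coherent choice and not a fault.
- **Week 24 status is reported elsewhere.** Table 14.2.3.17 counts subjects with more than 10 mmHg improvement by visit, and Table 14.2.3.18 analyses Week 24. The status is therefore not missing from the report. Those counts do not link visits within a subject, so they cannot separate a sustained response from a new or regained one.
- **Sparse visits.** With three post-baseline assessments, any rule is coarse. The midpoint rule still ties RR- with -RR at 112 and R-- with --R at 42, so it must be paired with a mark for ongoing response. It also credits days before response was seen: 14 for RRR, and 42 for --R.

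**Conclusion.** The concern holds within these limits. Read as first non-response after first response, the rule cannot register the Week 24 result. RR- equals RRR at 140 days, -R- equals -RR at 84 days, and a first response at Week 24 scores 0, the same as never responding.

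The day counts assume nominal visit days. The ties assume a Week 24 value is available; they survive the ±7-day windows and missing Week 4 or Week 12 values. For subjects who withdraw early, the SAP does not say which visit counts as the last one.

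The impact is minor. The endpoint is exploratory, summarised descriptively and outside the multiplicity procedure in SAP 5.4. Only Table 14.2.4.1 is affected, but it is the only duration output for the (A-a)DO2 part of a stated objective.

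**What to change.** Keep the endpoint as the first maintained response and reword the derivation in SAP 5.3.8:

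1. State that the second threshold is sought only at a visit after the first.
2. Date onset and first loss midway between the two adjacent available (A-a)DO2 assessments. On nominal days this gives the midpoint column in the working.
3. Treat subjects still in that first response at their last available double-blind (A-a)DO2 assessment as ongoing (censored) at that assessment, including those who withdraw early.
4. Tabulate the number ongoing, by arm, next to the durations in Table 14.2.4.1. This mark separates RR- from -RR and R-- from --R, which the days alone do not.

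Replacing the endpoint with total days in response is not needed. That is a different quantity, because it counts regained response.

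The cost is one reworded derivation and one program, with no new data. The downside is the midpoint convention, which assumes when between visits each change occurred.

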8.2 Inclusion Criteria

The patients must meet all of the following criteria to be eligible to enter the trial:

- aPAP diagnosed by CT, or by biopsy, or by Broncho Alveolar Lavage (BAL), and by increased GM-CSF autoantibodies in serum
- Stable or progressive aPAP (i.e. absolute VC not improved by more than 5% and/or DLCO not improved by more than 10% - assessed from medical records) during a minimum period of two months prior to the Baseline visit
- PaO₂ <75 mmHg/<10 kPa at rest, OR desaturation of >4 percentage points on the 6MWT
- An (A-a)DO₂ of minimum 25 mmHg/3.33 kPa
- Female or male ≥18 years of age
- Females who have been post-menopausal for >1 year or females of childbearing potential after a confirmed menstrual period using a highly efficient method of contraception (i.e. a method with <1% failure rate such as combined hormonal contraception, progesterone-only hormonal contraception, intrauterine device, intrauterine hormone-releasing system, bilateral tubal occlusion, vasectomised partner, sexual abstinence), during and until 30 days after last dose of trial treatment. Females of childbearing potential must have a negative serum pregnancy test at Screening (Visit 1) and a negative urine pregnancy test at dosing at Baseline (Visit 2) and must not be lactating
- Males agreeing to use condoms during and until 30 days after last dose of trial treatment, or males having a female partner who is using adequate contraception as described above
- Willing and able to provide signed informed consent
- Willing and able to comply with scheduled visits, treatment plan, laboratory tests, and other trial procedures specified in the protocol as judged by the investigator

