10.2.3 Exploratory Endpoints

10.2.3.1 Double-Blind Treatment Period

- Absolute change from baseline of (A-a)DO₂, VC (% predicted), DLCO (% predicted), FEV₁ (% predicted), FVC (% predicted), and relative change from baseline of PaO₂ after 4 and 12-weeks, treatment
- Time period during which the (A-a)DO₂ level is maintained below Baseline –10mmHg
- Number of subjects with improved tolerance to exercise (increase in distance walked ≥ 50 m or desaturation <4 percentage points on the 6MWT) after 4 and 12-weeks treatment
- Time period during which the improvement in tolerance to exercise is maintained
- Change from baseline in dyspnoea score and cough scores after 4 and 12-weeks treatment
- Number of subjects with improved QoL (change of ≥4 units on the SGRQ/number of subjects with 'no problems' in the EQ-5D-5L), after 4, 12, and 24-weeks treatment
- Change in serum concentration of biomarkers; KL-6, CEA, SP-A, SP-B, SP-C, SP-D, Cyfra 21-1 and LDH after 4, 12, and 24-weeks treatment
- Levels of anti-GM-CSF after 4, 12 and 24-weeks treatment
- Change in serum concentration of GM-CSF post first dose of trial drug and after 4-weeks treatment
- Number of subjects in need for oxygen supplement therapy during 24-weeks treatment
- The distribution of DSS at Screening and at Week 24
- The percentage of subjects with DSS 1 or 2 at Week 24

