All data will be tabulated using summary statistics including levels at each visit and change from baseline for continuous data, and counts and shifts including percentage of subjects within categories for frequency data. Tables will be based on all observed data applicable to the FAS population.

Number of WLLs over time

A Generalized Linear Model, based on the negative binomial distribution, is planned for analysis using the number of WLLs as the dependent variable and will include treatment group and the stratification factor of whether or not a WLL was conducted within 2 months prior to the Baseline (according to protocol version 4.0 and later versions), or whether or not WLL was conducted between the screening visit and the randomization visit (according to protocol versions before version 4.0), and country (Japan vs. all others) as fixed effects. The analysis will be adjusted for each subject's length of follow-up in the trial. The rate ratio (each active dose group: placebo) will be derived from the model along with the 95% 2-sided Confidence Intervals. Model adjusted mean rates for each treatment group will be derived. In this analysis each lung lavaged contributes as an event in the count per subject, regardless of whether both lungs are lavaged on different days or on the same day. Events with the date of criteria met in the double-blind period will be counted as being conducted in the double-blind period.

6 minute walking test (6MWT)

Each item related to the six minutes walk test (6MWT) will be summarized by visit. Summaries will include distance and duration of walk during the test, the pre and post walk Borg CR10, the derived change in dyspnoea score (post walk Borg CR10 score – pre walk Borg CR10 score), the SpO₂ at start and the worst SpO₂ during the walk, blood oxygen desaturation derived as (SpO₂ at start – Worst SpO₂ during the walk). Change from baseline after 24 weeks of treatment in; blood oxygen desaturation, difference in pre- to post-test dyspnoea score and distance and duration of walk will in addition be summarized separately including categorical variables corresponding to improved tolerance to exercise (derived as increase in distance walked ≥50 m (compared to baseline) or desaturation <4 percentage points on the 6MWT, respectively), see below.

CT scan

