- Number of subjects with >10 percentage points improvement in FEV₁ (% predicted) after 24-weeks treatment
- Number of subjects with >10 percentage points improvement in FVC (% predicted) after 24-weeks treatment
- Number of subjects with >10% relative improvement in PaO₂ after 24-weeks treatment
- Number of subjects with improved tolerance to exercise (increase in distance walked ≥50 m or desaturation <4 percentage points on the 6MWT) compared to baseline after 24-weeks treatment
- Number of subjects with improved CT score after 24-weeks treatment

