Table	14.2.3.34	Number of subjects with improved tolerance to exercise (desaturation < 4 percentage points on the 6MWT) by visit during 24 weeks treatment full analysis set		X					
Table	14.2.3.35	Analysis of number of subjects with improved tolerance to exercise (desaturation < 4 percentage points on the 6MWT) after 24 weeks treatment (Logistic regression)		X					
Table	14.2.3.36	Summary of Borg CR10 pre post and corresponding difference in walk dyspnea score and change from baseline in scores by visit during 24 weeks treatment		X					
Table	14.2.3.37	Analysis of change from baseline in dyspnea score after 24 weeks (ANCOVA)		X					
Table	14.2.3.38	Summary of cough (VAS) scores and change from baseline in cough scores by visit during 24 weeks treatment		X					
Table	14.2.3.39	Analysis of change from baseline in cough (VAS) scores after 24 weeks (ANCOVA)		X					
Table	14.2.3.40	Summary of number of subjects with Improved Worsened or No change in CT score during 24 weeks of treatment		X					
Table	14.2.3.41	Summary of CT Ground-Glass Opacification (GGO) score during 24 weeks of treatment		X					
Table	14.2.3.42	Analysis of number of subjects with Improved CT score compared to baseline after 24 weeks treatment (Logistic regression)		X					
Table	14.2.3.43	Summary of number of WLLs over time		X					
Table	14.2.3.44	Summary of details related to WLLs including reasons for, one or both lungs, and saline volume used.		X					
Table	14.2.3.45	Analysis of number of WLLs over time (negative binomial regression)		X					
Exploratory Efficacy Endpoints Double-Blind Treatment Period									
Table	14.2.4.1	Summary of time during which the (A-a)DO ₂ level is maintained below baseline (A-a)DO ₂ level -10 mmHg		X					
Table	14.2.4.2	Summary of time period during which the improvement in tolerance to exercise is maintained		X					
Table	14.2.4.3	Summary of SGRQ dimension scores and corresponding changes from baseline by visit during 24 weeks of treatment		X					
Table	14.2.4.4	Summary of number of subject with improved QoL score (improvement of at least 4 units on SGRQ total score) during 24 weeks of treatment		X					
Table	14.2.4.5	Summary of EQ-5D-5L dimension scores and corresponding shifts from baseline by visit during 24 weeks of treatment		X					
Table	14.2.4.6	Summary of Krebs von den Lungen-6 (KL-6) and change from baseline in Krebs von den Lungen-6 (KL-6) by visit during 24 weeks of treatment		X					

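### SAP 5.3.8 ends the exercise-improvement period on the condition that starts it and omits the edge-case rules; the desaturation wording also needs reconciling (exploratory and supportive outputs only)

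*SAP*

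**What the plan says.** The protocol lists as an exploratory double-blind endpoint the "Time period during which the improvement in tolerance to exercise is maintained" (section 10.2.3.1). In the same list, and in sections 10.2.2.2 and 12.1.7, improved tolerance is one category: a walk-distance gain of at least 50 m, or desaturation under 4 percentage points.

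SAP 5.3.8 makes the period operational using distance alone. It opens at the first visit where the gain from baseline is at least 50 m and closes at "the first visit where the increase in distance walked is above ≥ 50 m compared to baseline on the 6MWT". Nothing is said about subjects who never respond or who never lose the response. The output is Table 14.2.4.2 in SAP Appendix 1, "Summary of time period during which the improvement in tolerance to exercise is maintained".

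The (A-a)DO₂ period, defined in the same section, is handled differently. Its closing threshold is crossed in the opposite direction to its opening threshold. Subjects who never reach the first threshold get zero, and "for subjects never reaching the second threshold, the time period will be set to the duration" from the first qualifying visit to the last double-blind visit.

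For the desaturation part, the 6MWT paragraph of SAP 5.3.7 ties the comparison with baseline to distance only and then adds "or desaturation <4 percentage points on the 6MWT, respectively". SAP 5.3.8 does the same, for Weeks 4 and 12 and for the follow-up period. The list of categorical endpoints in SAP 5.3.7 instead puts the comparison after the whole bracket: "desaturation <4 percentage points on the 6MWT) compared to baseline after 24-weeks treatment". The general rule for further secondary endpoints promises "counts and shifts including percentage of subjects within categories for frequency data". Protocol 8.2 admits a subject on resting PaO₂ under 75 mmHg "OR desaturation of >4 percentage points on the 6MWT".

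**The concern.** A duration needs a closing condition that differs from its opening one. Here both are a gain of at least 50 m, so the first visit that satisfies the end is the visit that started the period. Programmed as written, the table carries no information.

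The natural repair, reading the end as a gain below 50 m, exposes a second gap. A subject who holds the gain to Week 24 never meets the end condition and gets no value, so the most durable responders would drop out of a summary of durability. What the table shows would then depend on an unrecorded programming choice.

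The desaturation issue is one of labelling. Desaturation is derived within a visit (starting SpO₂ minus worst SpO₂), so being under 4 points describes a state, not a change. A subject who enters on resting PaO₂ may already be under 4 at baseline and, on staying there, can be counted as improved. The two placements of the baseline comparison could lead two programmers to different counts.

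**Working it through.** **Inputs.** The walk test is done at Weeks 4, 12 and 24 after randomisation, nominal days 28, 84 and 168 (protocol Table 1). Let R mean a gain of at least 50 m at a visit and – mean no such gain. With all three visits attended there are 2³ = 8 patterns. The SAP states no figure to reproduce.

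**Rules compared.** Duration = day of end visit minus day of first R.

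1. As written: end = first visit with R.
2. Direction corrected only: end = first later visit with –.
3. Direction corrected plus the two (A-a)DO₂ edge rules: 0 if there is never an R; end = day 168 if the response is never lost.

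**Arithmetic.** 84 − 28 = 56; 168 − 84 = 84; 168 − 28 = 140; 168 − 168 = 0.

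| Weeks 4, 12, 24 | 1. As written | 2. Direction only | 3. With edge rules |
|---|---|---|---|
| R R R | 0 | no value | 140 |
| R R – | 0 | 140 | 140 |
| R – R | 0 | 56 | 56 |
| R – – | 0 | 56 | 56 |
| – R R | 0 | no value | 84 |
| – R – | 0 | 84 | 84 |
| – – R | 0 | no value | 0 |
| – – – | no value | no value | 0 |

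Rule 1 gives 0 days for all 7 responder patterns. Rule 2 leaves 4 of 8 without a value.

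**Can the text be rescued as it stands?** Suppose the end is the next later visit with R. Then RRR and RR– give 56, –RR gives 84, R–R gives 140 and the other four have no value. A subject who loses and regains the gain would score 140 days against 56 for one who never lost it, so this reading fails too.

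**What rule 3 leaves tied.** A first response at Week 24 and no response at all both score 0. RRR equals RR– at 140, and –RR equals –R– at 84. Table 14.2.3.32 already gives the number at or above 50 m by visit, so Week 24 status by arm is available. The split of the zeros is not stated in the plan.

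**Desaturation, side by side.** The 6MWT paragraph of SAP 5.3.7 and both places in 5.3.8 compare distance, but not desaturation, with baseline. The titles of Tables 14.2.3.32 to 14.2.3.35 follow that split: the distance titles refer to baseline and the desaturation titles do not. The categorical list in SAP 5.3.7 applies the comparison to both, with no rule for carrying it out. Appendix 1 names shift tables for DSS (14.2.4.23 and 14.2.4.25) but none for desaturation. SAP 5.1 lists neither the distance-only duration nor the splitting of the protocol's single either/or category into two components.

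**The case against.** The strongest reply is that this is a typing slip. The endpoint name speaks of an improvement being maintained, the neighbouring rule reverses its threshold, and any programmer would read below 50 m. The output is one exploratory, descriptive table, and the plan allows clarifications before unblinding. It is indeed probably a slip, and the scope is indeed narrow. But correcting the direction still leaves four patterns undefined. Protocol 12.1.8 defers rules for missing data, whereas never responding and never losing response are observed outcomes. SAP 5.2 provides a document for clarifications but supplies no rule.

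On desaturation, the reply is that the under-4 state comes from the protocol, that the logistic model includes the endpoint's own baseline covariate, and that desaturation is also summarised as a change from baseline (Table 14.2.3.31). All of that stands. It makes this a matter of labelling and consistency within a supportive output. The covariate does not, however, alter the counts and percentages labelled as improved.

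Two stronger readings are tempting. A reader might infer that subjects already under 4 points bias the comparison between arms. The documents do not give their number or how many stay under 4, so neither a size nor a direction can be claimed. A reader might also infer that no planned output will show baseline status. Only table titles are available, Table 14.2.3.34 is by visit, and individual walk-test data are listed (Listing 16.2.6.2). What can be said is that no desaturation shift table is named.

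**Conclusion.** The point holds and is minor. The duration rule in SAP 5.3.8 is wrong as written, with 0 days for all 7 responder patterns. It is incomplete once the direction is corrected, with no value for 4 of 8 patterns. These counts assume complete visits on nominal days and a period confined to the double-blind phase; actual visit dates would shift the days but not the pattern.

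The desaturation wording is inconsistent between places in the SAP and allows a subject who was already under 4 points to be counted as improved. No effect on the arm comparison is established.

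A reader might go further and doubt the walk-distance results generally. That does not follow. The duration is exploratory, the responder categories are supportive, and neither enters the testing procedure in SAP 5.4. The primary endpoint, the key secondary 6MWD analysis and the at-least-50 m responder count are unaffected.

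**What to change.** For the duration (SAP 5.3.8):

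- End the period at the first later visit with a gain below 50 m.
- Set it to 0 for subjects who never respond.
- Use the last double-blind visit for subjects who never lose the response.
- In Table 14.2.4.2, report first responses at Week 24 separately from never-responders, and refer to Table 14.2.3.32 for Week 24 status by arm.

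For desaturation (SAP 5.3.7, 5.3.8 and Appendix 1):

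- Use one wording throughout for what is compared with baseline.
- Label the SAP's desaturation component as desaturation under 4 points at the visit.
- Name in Appendix 1 the baseline-to-visit shift (under 4, or 4 and above) that the general rule for frequency data already promises.

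In SAP 5.1, state that the duration uses distance only and that the protocol's single either/or category is analysed as two components.

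The cost is a few lines of SAP text, one corrected derivation, one split row and one shift table. It needs no new data and has no effect on alpha. If the SAP is not re-issued, the wording can go into the pre-analysis review document described in SAP 5.2, signed before unblinding.
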